9.3.2. Columbia Suicide Severity Rating Scale (C-SSRS)

The frequency and percentage of subjects with each response for suicidal ideation, intensity of ideation, and suicidal behavior items will be summarized for the treatment period. The distribution of responses for most severe suicidal ideation and suicidal behavior will also be presented for the treatment period.

- 1. The counting method of suicidal ideation:
- In each period (lifetime and treatment), the subject who has at least one of each suicidal ideation 5 items will be counted once. In case subjects report suicidal ideation several times within a period, then the subject will be counted in the most severe suicidal ideation item.
- 2. The counting method of suicidal behavior:
- In each period (lifetime and treatment), the subject who has at least one of each suicidal behavior 5 items and non-suicidal self-injurious behavior item will be counted once. In case subjects will report suicidal behavior with non-suicidal self-injurious behavior several times within a period, then the subject will be counted in the most severe suicidal behavior item.
- 3. The counting method of suicidal ideation or suicidal behavior In each period (lifetime and treatment) the subjects who meet the criteria of (1) or (2) will

Mitsubishi Tanabe Pharma America, Inc.

be counted.

4. The counting method of non-suicidal self-injurious behavior item
In each period the subjects who have non-suicidal self-injurious behavior item will be counted.

9.3.3. Laboratory Tests

Only central laboratory data and change from baseline (haematology, biochemistry or urinalysis) will be summarized with descriptive statistics (continuous variables) or as distributions (categorical variables) by visit except for pregnancy test parameter. For urinalysis parameter, a shift table from baseline will be presented.

The categories for out of reference range will be Low, Normal and High for Hematology, Biochemistry, Urinalysis and , and Normal and Abnormal for Urinalysis (Qualitative Value). For these categories, a shift table from baseline to each visit up to A04 Week 96 will be presented.

Laboratory test values will be considered potentially clinically significant (PCS) if they meet either the low or high PCSV criteria listed in section 8.3.3.3. A shift table describing the number and percentage of subjects shifting from non PCSV at baseline to PCSV at post-baseline will be performed any time during treatment period.

The percentages will be calculated from the number of subjects with available baseline values and any time post-baseline value.

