7. STATISTICAL CONSIDERATIONS

7.1. Descriptive Statistics

Data listings will be sorted by center and subject number (and by visit, if applicable). Continuous data will be summarized descriptively using the number in the analysis set (N), the number of observations (n), mean, standard deviation (SD), median, minimum and maximum. Categorical data will be summarized using frequency counts and percentages. The denominator for the percentages will be the total number of subjects in the treatment group and analysis set being presented, unless otherwise specified. For visit-specific data, the number of subjects with non-missing observations at the visit in question will be used as the denominator for percent calculations. Unknown, Not Done, Not Applicable and other classifications of missing data will not be considered.

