8.3.3.3. Laboratory Tests

Hematology tests will include: Red blood cell count, hemoglobin, hematocrit value, white blood cell count with differential and platelet count.

Blood Chemistry will include: Albumin, Total protein, aspartate aminotransferase (AST), alanine aminotransferase (ALT), lactate dehydrogenase (LDH), alkaline phosphatase (ALP), total bilirubin, direct bilirubin, c-reactive protein (CRP), creatine kinase (CK), total cholesterol, triglycerides, blood urea nitrogen (BUN), bicarbonate, serum glucose, serum creatinine level, uric acid, sodium (Na), potassium (K), chloride, calcium (Ca), cystatin-C and Vitamin B6.

Note: In addition, GGT will be obtained in only Japan country.

Qualitative urinalysis will include: Protein, glucose, occult blood, white blood cells, urobilinogen, and bilirubin.

Pregnancy test (WOCP only): For women subjects with Childbearing Potential only, serum beta-human chorionic gonadotropin (hCG) level or urine dipstick will be conducted.

Laboratory values below the limit of quantification

Laboratory values below 1/2 LLOQ (lower limit of quantification) will be used for BLQ (below the limit of quantification) for data summary statistics.

Handling of Reference Values and Indeterminate Values for Clinical Laboratory Test Parameters

If laboratory test value or its reference is indeterminate due to a problem with the test sample, then this value will be handled as a missing value.

Criteria for Potentially Clinically Significant Values (PCSV for laboratory):

The following criteria will be defined 8,9

Chemistry

- ALT $>= 3 \times \text{Upper Limit of Normal Range (ULN)}, 5 \times \text{ULN}, 10 \times \text{ULN}, 20 \times \text{ULN}$
- AST $>= 3 \times ULN$, $5 \times ULN$, $10 \times ULN$, $20 \times ULN$
- ALT and/or AST >= 3 \times ULN, $5\times$ ULN, $10\times$ ULN, $20\times$ ULN
- Total Bilirubin $\geq 2 \times ULN$

Mitsubishi Tanabe Pharma America, Inc.

- ALP >400 U/L
- ALT or AST > $3 \times ULN$ with Total Bilirubin > $1.5 \times ULN$
- ALT or AST $> 3 \times ULN$ with Total Bilirubin $> 2 \times ULN$
- Hy's law (ALT or AST > $3 \times ULN$ and ALP < $2 \times ULN$ and Total Bilirubin >= $2 \times ULN$)
- LDH $>= 3 \times ULN$
- BUN >= 30 mg/dL
- Serum Creatine >= 2.0mg/dL
- Uric acid Male >10.0 mg/dL, Female >8.0 mg/dL
- $CK \ge 3$ x upper limit of normal
- Chloride (Low) $\leq 90 \text{ mEq/L}$
- Chloride (High) ≥ 118 mEq/L
- Potassium (K) (Low) <3.0 mmol/l
- Potassium (K) (High) >5.5mmol/1

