- Sodium (Na) (Low) <130mmol/1
- Sodium (Na) (High) ≥ 150 mmol/l
- Calcium (Ca) (Low) <7.0 mg/dL
- Calcium (Ca) (High) ≥ 12 mg/dL
- Concurrent Hepatic Abnormality;
- ALT or AST > $3 \times$ ULN with Total Bilirubin > $1.5 \times$ ULN
- ALT or AST > $3 \times$ ULN with Total Bilirubin > $2 \times$ ULN
- Hy's law (ALT or AST > $3 \times$ ULN and ALP < $2 \times$ ULN and Total Bilirubin >= $2 \times$ ULN)

Hematology

- Hematocrit:
 - Male ≤ 37 % and decrease of ≥ 3 percentage points from baseline,
 - o Female <=32 % and decrease of ≥ 3 percentage points from baseline
- Hemoglobin:
 - o Male ≤ 11.5 g/dL,
 - o Female ≤ 9.5 g/dL
- White blood count (Low) $\leq 2800/\text{mm}3$
- White blood count (High) ≥ 16,000/mm3
- Neutrophils Absolute count < 1,000/mm3
- Platelet count (Low) $\leq 100,000/\text{mm}$ 3
- Platelet count (High) ≥ 700,000/mm3

Mitsubishi Tanabe Pharma America, Inc.

8.3.3.4. 12-Lead ECG

A 12-lead ECG will be performed after the subject has rested for at least 5 minutes in a supine position. The ECG will include the following numerical measurements: HR, R wave to R wave (RR) interval, heart rate, QRS, QT, QTcB, and QTcF. The Investigator will perform an overall evaluation of the ECG for safety purposes and the recording will be reported as 'normal', 'abnormal CS', or 'abnormal NCS'

The RR, QTcF and QTcB will be calculated using the below formulas, regardless if collected in CRF.

- RR (msec) will be calculated as {60 / heart rate (beats/min)} *1000 and reported to integer.
- QTcF (msec) and QTcB (msec) will be calculated as {QT (sec) / RR (sec) ^ (1/3)} * 1000 and {QT (sec) / RR (sec) ^ (1/2)} *1000 respectively and reported to integer.

Criteria for Potentially Clinically Significant Values (PCSV for 12-Lead ECG):

- HR at post-baseline <=50 bpm and decrease from baseline >=20 bpm
- HR at post-baseline >=120 bpm and increase from baseline >=20 bpm
- PR at post-baseline >=220 msec and increase from baseline >=20 msec
- QRS at post-baseline >= 120 msec and QRS at baseline < 120 msec
- Baseline OTc <=450 msec and QTc >450 msec at post-baseline
- Baseline QTc <=480 msec and QTc > 480 msec at post-baseline
- Baseline QTc <=500 msec and QTc > 500 msec at post-baseline
- Change from baseline at post-baseline in QTc > 30 msec
- Change from baseline at post-baseline in QTc > 60 msec

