9.3.4. Vital Signs

Vital sign measurements and their changes from baseline will be summarized using descriptive statistics by visit. Those parameters will include: heart rate (HR), supine and standing blood pressure (BP) (both systolic and diastolic), body temperature and weight. Furthermore, supine minus standing blood pressure (both systolic and diastolic) and their change from baseline will be summarized with descriptive statistics by visit.

Vital sign values will be considered PCSV if they meet both criteria of the observed value and the change from baseline listed in section 8.3.3.5. A shift table describing the number and percentage of subjects shifting from non PCSV at baseline to PCSV at any time post-baseline will be performed during treatment period. The percentages will be calculated from the number of subjects with a baseline value and any time post-baseline value

9.3.5. 12-Lead ECGs

The ECGs will be assessed by the investigator and deemed "Normal", "Abnormal, not clinically significant" (Abnormal, NCS) and "Abnormal, clinically significant" (Abnormal, CS) and

Mitsubishi Tanabe Pharma America, Inc.

tabulated by visit using frequency counts and percentages.

In addition, the numerical ECG parameters and their change from baseline generated by the central ECG laboratory (see section 8.3.3.4) will be summarized by descriptive statistics for each parameter by visit.

ECG parameters values will be considered PCSV if they meet the criteria listed in section 8.3.3.4. The number and percentage of subjects with PCSV will be tabulated. The percentages are to be calculated from the number of subjects with available baseline values and any time post-baseline value for a specific category.

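### Laboratory shift percentages in SAP 9.3.3 are diluted by subjects already potentially clinically significant at baseline, who cannot shift

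*SAP*

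**What the plan says.** SAP 9.3.3 (Laboratory Tests) plans a shift table giving the "number and percentage of subjects shifting from non PCSV at baseline to PCSV at post-baseline", taken over the whole treatment period. The next paragraph sets the denominator: "The percentages will be calculated from the number of subjects with available baseline values and any time post-baseline value". It requires that both values exist and sets no condition on what the baseline value is.

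The general rule in SAP 7.1 does not narrow this: "The denominator for the percentages will be the total number of subjects in the treatment group and analysis set being presented, unless otherwise specified". Baseline is the last valid value before the first dose in MT-1186-A02 (SAP 8.1).

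The criteria are in SAP 8.3.3.3. Most are absolute limits or multiples of the upper limit of normal (ULN), for example "Uric acid Male >10.0 mg/dL, Female >8.0 mg/dL". Those for ALT, AST, bilirubin, ALP, LDH, BUN, creatinine, CK, electrolytes, hemoglobin, white cells, neutrophils and platelets are of the same kind. Hematocrit differs because it also needs a fall, for example "Female <=32 % and decrease of ≥ 3 percentage points from baseline".

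For ECGs, SAP 8.3.3.4 writes a baseline condition into the QRS criterion and the QTc threshold criteria, for example "Baseline QTc <=480 msec and QTc > 480 msec at post-baseline". SAP 9.3.5 then says: "The percentages are to be calculated from the number of subjects with available baseline values and any time post-baseline value". That sentence goes on to tie the denominator to a specific category, without saying what a category is.

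**The concern.** The event is a change of state, from non-PCSV to PCSV. Only a subject who starts as non-PCSV can have it. A subject who starts as PCSV stays in the denominator whatever happens later and contributes nothing to the numerator. The percentage is therefore lower than the percentage among those who could have the event, and the error has only one direction.

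Safety and tolerability is the study's only secondary objective (protocol 7.1.2, SAP 3.1.2). Under SAP 5.2 there will be no final analysis, so the interim tables are the ones planned for this study. A reader who takes a printed shift percentage as the risk of a new abnormality would read it slightly too low, by an amount that the table, as described, does not let them work out.

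**Working it through.** The plan gives no figure for this table, so there is nothing to reproduce. The size follows from algebra.

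**Inputs**
- Numerator x: subjects non-PCSV at baseline who become PCSV (SAP 9.3.3).
- Denominator N: subjects with a baseline and any post-baseline value (SAP 9.3.3).
- b: share of N already PCSV at baseline. The documents do not give it. The MT-1186-A04 exclusion criteria (protocol 9.4) contain no laboratory limit, but baseline is taken at entry to MT-1186-A02, whose entry criteria are not in these documents. The range below is therefore assumed.
- For scale only: 384 randomized (SAP 4.2), taken as 384 / 2 = 192 per arm, assuming an equal split and complete data.

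**Formula**
- SAP percentage = x / N.
- At-risk percentage = x / [N(1 - b)].
- So SAP percentage = at-risk percentage × (1 - b), and the relative understatement is exactly b.

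**Results**

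| Assumed b | At-risk rate 10% prints as | At-risk rate 5% prints as |
|---|---|---|
| 0% | 10.0% | 5.0% |
| 1% | 0.10 × 0.99 = 9.9% | 0.05 × 0.99 = 4.95% |
| 5% | 0.10 × 0.95 = 9.5% | 0.05 × 0.95 = 4.75% |
| 10% | 0.10 × 0.90 = 9.0% | 0.05 × 0.90 = 4.5% |
| 20% | 0.10 × 0.80 = 8.0% | 0.05 × 0.80 = 4.0% |

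In subjects: with 192 per arm and b = 10%, about 19 are already PCSV and 173 are at risk. A 10% at-risk rate gives 17.3 expected shifts, and 17.3 / 192 = 9.0%.

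**Comparison between arms**
- Equal b: the factor (1 - b) cancels in the ratio, and the difference shrinks by (1 - b). At b = 20%, at-risk rates of 10% and 5% print as 8% and 4%. The ratio is still 2, and the difference is 4 points instead of 5.
- Unequal b, 10% against 5%, with equal at-risk rates: ratio 0.90 / 0.95 = 0.947 instead of 1. At a 10% rate the arms print as 9.0% and 9.5%.

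**Which criteria are affected**
- Laboratory criteria that are absolute limits or ULN multiples: affected whenever b is above zero.
- Hematocrit: not affected. It requires a fall of at least 3 percentage points from baseline, so no one meets it at baseline.
- ECG QRS and QTc thresholds: these carry a baseline condition. Whether the denominator matches it depends on how the closing reference to a category in SAP 9.3.5 is read.

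**The case against.** The best defence is that this is a convention, stated openly. Dividing every cell of a shift table by the same number of evaluable subjects makes the cells add to 100%, and it gives a valid quantity: the share of evaluable subjects who newly became PCSV. That stands as far as it goes. However, SAP 9.3.3 describes only the shift from non-PCSV to PCSV and does not commit to showing the number already PCSV at baseline. Without that number the at-risk percentage cannot be recovered from the table.

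Three stronger readings are tempting, and the documents do not support them.

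- *New laboratory abnormalities go unreported.* They do not. The number shifting is printed and is correct. SAP 9.3.3 also gives low/normal/high shift tables by visit, and clinically significant laboratory results are recorded as adverse events (protocol 15.5) and so reach the summaries in SAP 9.3.1.
- *The comparison of arms is distorted.* This needs b to differ between randomized arms. A gap as wide as 10% against 25% would turn equal 10% rates into 9.0% and 7.5%. With 192 per arm, that gap is 0.15 / √(0.175 × 0.825 × 2 / 192) = 0.15 / 0.0388, or about 3.9 standard errors, so chance is very unlikely to produce it for a given parameter.
- *The ECG table has the same fault.* The reference to a specific category in SAP 9.3.5 may already limit the denominator to subjects in the relevant baseline category. The wording is ambiguous, and an error is not established.

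It is also fair to say that many of these criteria, such as ALT at 10 or 20 × ULN, may rarely be met before dosing, in which case the effect is negligible. The documents contain no data to settle this either way.

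**Conclusion.** The point holds for the laboratory table, as a minor one. As written, SAP 9.3.3 keeps in the denominator subjects who cannot have the event, and nothing in SAP 7.1, 8.3.3.3 or 9.3.3 removes them. The relative understatement equals the baseline PCSV share for each criterion. That share is unknown from the documents, so every size given here rests on an assumed b. If b is zero, the two denominators agree.

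The percentages are descriptive, and the SAP attaches no test or decision rule to them. The case for changing the denominator is that it answers the question the table asks and costs almost nothing. For ECGs the conclusion is only that the wording should be made explicit.

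**What to change.** In SAP 9.3.3, replace the denominator sentence with one saying that, for each laboratory criterion and treatment arm, percentages use subjects who are non-PCSV on that criterion at baseline and have at least one post-baseline value. Apply it to each criterion separately, so that low and high limits and each ULN multiple have their own denominator. Print that denominator, and add a row with the number already PCSV at baseline. For hematocrit, the rule leaves the percentage unchanged.

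In SAP 9.3.5, state that for the QRS criterion and the QTc threshold criteria the category means subjects who meet the stated baseline condition.

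The cost is two sentences and a denominator change in the table programs. No new data are needed and no efficacy analysis is touched. SAP 2 allows an update before database lock. After that, the change can be described and justified in the clinical study report, where the same section places deviations from the planned analysis.

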9.3.4. Vital Signs

Vital sign measurements and their changes from baseline will be summarized using descriptive statistics by visit. Those parameters will include: heart rate (HR), supine and standing blood pressure (BP) (both systolic and diastolic), body temperature and weight. Furthermore, supine minus standing blood pressure (both systolic and diastolic) and their change from baseline will be summarized with descriptive statistics by visit.

Vital sign values will be considered PCSV if they meet both criteria of the observed value and the change from baseline listed in section 8.3.3.5. A shift table describing the number and percentage of subjects shifting from non PCSV at baseline to PCSV at any time post-baseline will be performed during treatment period. The percentages will be calculated from the number of subjects with a baseline value and any time post-baseline value

9.3.5. 12-Lead ECGs

The ECGs will be assessed by the investigator and deemed "Normal", "Abnormal, not clinically significant" (Abnormal, NCS) and "Abnormal, clinically significant" (Abnormal, CS) and

Mitsubishi Tanabe Pharma America, Inc.

tabulated by visit using frequency counts and percentages.

In addition, the numerical ECG parameters and their change from baseline generated by the central ECG laboratory (see section 8.3.3.4) will be summarized by descriptive statistics for each parameter by visit.

ECG parameters values will be considered PCSV if they meet the criteria listed in section 8.3.3.4. The number and percentage of subjects with PCSV will be tabulated. The percentages are to be calculated from the number of subjects with available baseline values and any time post-baseline value for a specific category.

9.3.6. Physical Examinations

Physical examination will be listed for each visit in MT-1186-A04.

Mitsubishi Tanabe Pharma America, Inc.

9.4. Subgroup analysis

The following subgroups will be analyzed for the time to at least 12-point decrease in ALSFRS-R or death (the primary endpoint) and time to death, tracheostomy, or permanent assisted mechanical ventilation endpoints (the secondary endpoint). For the time to event endpoints, the same Cox proportional hazard regression model will be used while adding the subgroup variable as well as the subgroup by treatment interactions. The influence of each subgroup factor will be investigated using the p-values for the interaction terms. The subgroup analysis will be performed on the Randomized set. In addition, forest plot depicting the treatment effect and 95% CI for all subgroups will be displayed for the time to at least 12-point decrease in ALSFRS-R or death and the time to death, tracheostomy, or permanent assisted mechanical ventilation.

Note: In some subgroup analyses, some factors will be statistically adjusted (e.g., in the country subgroup analysis, the Region factor will be removed).

- Race (White; Black; Asian; Other)
- Age (>=65 years old; <65 years old)
- Region (North America; Europe; Asia)
- Body Weight at baseline in MT-1186-A02 (>=Median; <Median)
- BMI at baseline in MT-1186-A02 (>=Median; <Median)
- Country (United States; Canada; Germany; Italy; Switzerland; Japan; South Korea)
- Disease duration from onset of symptoms (<1 year; >=1 year)
- ALSFRS-R score at baseline in MT-1186-A02 (>=Median, <Median)
- ALSFRS deterioration strata for randomization (-1, -2; -3, -4)
- Initial symptom (Bulbar; Limb)
- El Escorial revised Airlie House Diagnostic Criteria (Definite ALS; Probable ALS)
- Concomitant use of riluzole (Present; Absent)
- Concomitant use of AMX0035 (Present; Absent)
- %FVC at baseline in MT-1186-A02 (>=80%, <80%)
- %SVC at baseline in MT-1186-A02 (>=80%, <80%)

Mitsubishi Tanabe Pharma America, Inc.

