8.3.1.2. Demographic and Other Baseline Characteristics

8.3.1.2.1. Demographics:

This data not collected in MT-1186-A04 will be taken from MT-1186-A02.

Continuous: age, height, weight, Body Mass Index (BMI);

Categorical: age categorized as \leq 64 years versus \geq 65 years, and \leq 19, 20–29, 30–39, 40–49,

Mitsubishi Tanabe Pharma America, Inc.

50–59, 60–69, ≥ 70, gender, race, ethnicity, country and region defined as America- AM, Europe -EU and Asia Pacific - AP

O BMI will be calculated as weight at screening (kg) / {height at screening (m)}² and reported to 1dp.

Table 2: Demographic and Baseline Characteristics

Category	Item	Type of Data	Definition/Breakdown
	Gender	Binary	Male, Female
	Race	Categorized	 White Black or African American Asian – Japanese Asian - Not Japanese American Indian or Alaska Native Native Hawaiian or Pacific Islander Not Reported Other
Demography		Continuous	
	Age (year)	Categorized	\leq 19, 20–29, 30–39, 40–49, 50–59, 60–69, \geq 70
		Categorized (binary)	<65, ≥ 65
	Height (cm)	Continuous	
	Body weight (kg)	Continuous	
	BMI	Continuous	Weight at screening (kg) / {height at screening (m)} ²
	Country	Categorized	United States, Canada, Germany,
			Italy, Switzerland, Japan, South
			Korea
	Region	Categorized	1. America-AM
	•		2. Europe -EU
			3. Asia Pacific - AP
	Ethnicity	Categorized	1. Hispanic or Latino
			2. Not Hispanic or Latino
			3. Not Reported
			4. Unknown

Mitsubishi Tanabe Pharma America, Inc.

8.3.1.2.2. ALS History:

This data not collected in MT-1186-A04 will be taken from MT-1186-A02.

Continuous:

- (1) Disease Duration from Onset of Symptoms (years) and from ALS Diagnosis (years),
- (2) ALSFRS-R score at screening,
- (3) ALSFRS-R at Baseline,

Categorical:

- (1) ALSFRS-R Deterioration Rate of (-1,-2) or (-3,-4),
- (2) Disease duration from Onset of Symptoms categorized at <1 year vs ≥ 1 year and from Onset of ALS Diagnosis categorized at <1 year vs ≥ 1 year,
- (3) Initial symptom categorized as 'Bulbar onset' or 'Limb onset',
- (4) ALS Diagnosis categorized 'Sporadic' or 'Familial',
- (5) Categorical El Escorial revised Diagnostic,
- (6) Concomitant use of riluzole 'Present' or 'Absent',
- (7) Previous use of AMX0035 'Present' or 'Absent',
- (8) Concomitant use of AMX0035 'Present' or 'Absent',

Table 3: ALS History Parameters

Category	Item	Type of Data	Definition/Breakdown
	Disease duration from Onset of	Continuous	(Date of Screening - Date of Onset of Symptoms*)/365.25

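### SAP 9.4 tests effect modification by seven continuous baseline variables on two-way splits; a pre-specified continuous interaction would be a cheap and usually more powerful main test

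*SAP*

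**What the plan says.** SAP 9.4 (Subgroup analysis) covers the primary endpoint and time to death, tracheostomy or permanent assisted ventilation, on the Randomized set. The method is that "the same Cox proportional hazard regression model will be used while adding the subgroup variable as well as the subgroup by treatment interactions". The criterion is: "The influence of each subgroup factor will be investigated using the p-values for the interaction terms". In addition, a "forest plot depicting the treatment effect and 95% CI for all subgroups will be displayed" for both endpoints.

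Seven of the 15 listed factors are continuous measures split in two:

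- three at the sample median: "Body Weight at baseline in MT-1186-A02 (>=Median; <Median"), "BMI at baseline in MT-1186-A02 (>=Median; <Median") and "ALSFRS-R score at baseline in MT-1186-A02 (>=Median, <Median");
- four at a fixed value: "Age (>=65 years old; <65 years old"), disease duration from symptom onset at 1 year, and %FVC and %SVC each at 80%.

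SAP 8.3.1.2 itself treats several of these as continuous ("Continuous: age, height, weight, Body Mass Index (BMI"), and its ALS history list adds disease duration and baseline ALSFRS-R). In SAP 9.2.1.1, baseline ALSFRS-R enters the Cox model as a covariate, but only as a main effect. No visible text plans a treatment interaction with any of the seven on its measured scale.

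**The concern.** A two-way split suits a forest plot, but as a test it treats a subject just above the cut like one far above it. If the advantage of daily dosing changes gradually with, say, baseline ALSFRS-R or %SVC, the split test is more likely to miss it than a test on the measured value in the same subjects. Interaction tests have little power at this event count in any case, and a non-significant interaction p-value is easily read as absence of influence. SAP 5.2 says no final analysis will be conducted, so more data cannot make up for an inefficient test.

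**Working it through.** **1. The plan's own figure.** Inputs from Protocol 17.2 and SAP 4.2: 190 per group, control event-free rate 65% at Week 48, hazard ratio 0.775, 2-sided alpha 20%, stated power 70%. Assume exponential times, no dropout and 96 weeks in all.

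- Control event-free at 96 weeks: 0.65² = 0.4225. Daily group: 0.4225^0.775 = 0.513.
- Events: 190 × (1 − 0.4225) + 190 × (1 − 0.513) = 202.3.
- Power (Schoenfeld): 70.2%, which reproduces the 70%. Follow-up of 48 weeks alone gives 120.4 events and 54.7%.

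The documents give no power for the interactions.

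**2. Information kept by a split.** With a linear interaction, the efficiency of a split at c relative to the measured value is corr(X, 1[X ≥ c])². For a normal X with proportion p on one side this is φ(z_p)² / (p(1 − p)).

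| Split, normal X | Kept | Lost |
|---|---|---|
| 50/50 (= 2/π) | 63.7% | 36.3% |
| 40/60 | 62.2% | 37.8% |
| 30/70 | 57.6% | 42.4% |
| 25/75 | 53.9% | 46.1% |
| 20/80 | 49.0% | 51.0% |

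At a median split, 202.3 events are worth 202.3 × 0.637 ≈ 129.

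**3. Other shapes.** The documents give no distribution for any of the seven variables, so a range is needed. Loss at a median split: uniform 25%, normal truncated at ±1 SD 27%, beta(2,2) 30%, beta(5,2) 35%, lognormal (sigma 0.4) 44%, exponential 52%. If the effect is a step at the cut, the split loses nothing and the linear term is the weaker test, with efficiency 0.64 for a normal X cut at its median.

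**4. Power.** Assume a ratio of hazard ratios of 1.3 per SD, so b = ln 1.3 = 0.262. With D events and efficiency e, the expected z is b × √(D × e / 4). At D = 202.3 this is 1.866 continuous, 1.489 median split and 1.369 for 75/25. Comparing these with 1.96 and 1.28 (2-sided) gives the first two columns. SAP 9.4 sets no level for the interaction test, so both of the plan's nominal levels are shown.

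| Test | 5% level, 202 events | 20% level, 202 events | 5% level, 120 events |
|---|---|---|---|
| Continuous value | 46% | 72% | 30% |
| Median split | 32% | 58% | 21% |
| 75/25 split | 28% | 54% | 18% |

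Using 204 events changes these by less than half a percentage point. Simulated Cox models (1,500 trials, about 203 events, normal X, median split) gave 46% v 32% at the 5% level and 71% v 57% at the 20% level. With a uniform X they gave 45% v 35% and 73% v 64%. With no interaction, both tests rejected at 20% and at 5–6%, so the gain is not bought with false positives.

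**5. Other interaction sizes.** At 202.3 events and the 5% level, for a normal X and a median split, power is 30% v 21% at b = 0.2, 57% v 40% at b = 0.3 and 81% v 62% at b = 0.4.

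**The case against.** **The 36% is not a floor.** A reader might infer that at least 36% of the information is always thrown away. The documents do not support that. The figure needs a roughly normal variable and a linear interaction. ALSFRS-R is bounded at 48 (SAP 8.3.2.1), and the A02 entry criteria, which could truncate these variables, are not in the documents.

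**P-values are not the only output.** The same section plans effect estimates with 95% CIs for all subgroups. This is correct, but they come from the same splits and recover none of the lost information, and the interaction p-value remains the stated criterion.

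**The assumed interaction is large.** A ratio of 1.3 per SD around 0.775 implies hazard ratios of about 0.60 at −1 SD, 1.01 at +1 SD and 1.31 at +2 SD. Nothing in the documents supports that size. The comparison between tests does not depend on it, but the absolute powers do.

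**Events may be fewer.** SAP 4.1 and 5.1–5.2 record that both studies were stopped, and SAP 4.2 that 202 of 384 randomized subjects had entered A04. At 120 events both tests are weak. This stands for absolute power; the percentage of information lost is unchanged.

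**The planned subgroups are legitimate.** The cuts are pre-specified or are medians that do not depend on outcome, so they introduce no bias. The analyses are supportive, without type I error control (SAP 7.2). This also stands, and it limits the weight of the point.

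**A linear test has its own assumption.** A plot with two categories cannot check it, because two points always fit a line. Any fix therefore needs a separate check.

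**Conclusion.** The point holds as an inefficiency in a supportive analysis. It is not an error and does not touch the primary result. For seven factors, the stated test of effect modification uses two-way splits and the forest plots add nothing beyond them.

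Under a roughly linear interaction, a median split costs about 36% for a roughly normal variable and about 25% for a flat one. For symmetric variables off-centre cuts cost more, and for strongly right-skewed variables the median split itself can cost 44–52%. There is no loss if the effect steps at the cut. With the assumed ratio of 1.3 per SD and about 202 to 204 events, this means some 14 percentage points of power for a normal variable split at its median, and about 18 for a 75/25 split. Part of the SAP's code and text is not shown, so a continuous interaction elsewhere cannot be excluded, but section 9.4 reads as complete without one.

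**What to change.** In SAP 9.4, before database lock:

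1. Keep the categories, their interaction terms and the forest plots. Leave the truly categorical factors as they are.
2. For the seven continuous factors, name the treatment by continuous baseline value interaction, in the same Cox model, as the main test of effect modification. Report the ratio of hazard ratios per SD with its CI.
3. Check linearity with a spline or quadratic interaction term, or with three or more categories. Consider a log transform for skewed variables such as disease duration, so that extreme values do not drive the result.
4. State which p-value comes from which model, because the continuous test will stand beside subgroup estimates from the split model.

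The cost is seven main model statements for each of two endpoints, plus the linearity checks, on baseline values the planned splits already need. For ALSFRS-R the continuous value is already in the model, so only a product term is added. The downside is the assumption of an approximately linear change in the log hazard ratio: if the effect truly steps at the cut, the continuous test is the less efficient one, and the retained split results would show the effect better.
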